4.4. Permanent Discontinuation of Study Therapy

An individual subject will not receive any further investigational product if any of the following occur in the subject in question:

Withdrawal of consent or lost to follow-up

Adverse event that, in the opinion of the investigator or the sponsor, contraindicates further dosing

Subject is determined to have met one or more of the exclusion criteria for study participation at study entry and continuing investigational therapy might constitute a safety risk

Pregnancy or intent to become pregnant

Any AE that meets criteria for discontinuation as defined in Section 9.3.

- Serious Adverse event related to thoracic radiation, with the exception of toxicities that do not meet the criteria for discontinuation as defined in Section 9.3.
- Dose-limiting toxicity (See Section 6.3 for definition of DLT).
- Grade ≥ 3 infusion reaction

18 Nov 2020 Page **64** of **164**

- Subject noncompliance that, in the opinion of the investigator or sponsor, warrants withdrawal; e.g., refusal to adhere to scheduled visits
- Initiation of alternative anticancer therapy including another investigational agent
- Confirmation of PD and investigator determination that the subject is no longer benefiting from treatment with durvalumab
 + tremelimumab

Subjects who are permanently discontinued from further receipt of investigational product, regardless of the reason (withdrawal of consent, due to an AE, other), will be identified as having permanently discontinued treatment.

Subjects who are permanently discontinued from receiving investigational product will be followed for safety per Section 9.0 and Appendix 2 or 3, including the collection of any protocol-specified blood specimens, unless consent is withdrawn or the subject is lost to follow-up or enrolled I another clinical study. All subjects will be followed for survival. Subjects who decline to return to the site for evaluations will be offered follow-up by phone every 3 months as an alternative.

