6.3. Definition of Dose Limiting Toxicity (DLT)

Dose-limiting toxicities (DLTs) will be evaluated from the first day of administration of durvalumab (cohort 1) or durvalumab+tremelimumab (cohort 2), in this trial. The period for evaluating DLTs will be from the day of first administration of study therapy until 30 days after surgical resection or 100 days following the last dose of study therapy, whichever occurs later. Subjects who do not remain on the study up to this time for reasons other than DLT will be replaced with another subject. Grading of DLTs will follow the guidelines provided in the Common Terminology Criteria for Adverse Events (CTCAE) version 4.0. A patient who experiences a DLT will be permanently discontinued from treatment and will proceed to surgery after standard preoperative evaluation by a surgeon and anesthesiologist. Prior to surgery any treatment related toxicity should have resolved to ≤grade 1. [5]

A DLT will be defined as any Grade 3 or higher toxicity that occurs during the DLT evaluation period. Toxicity that is clearly and directly related to the primary disease or to another etiology is excluded from this definition. The following will be DLTs:

- Any Grade 4 irAE
- Any ≥ Grade 3 colitis
- Any Grade 3 or 4 non-infectious pneumonitis irrespective of duration
- Any Grade 2 pneumonitis that does not resolve to ≤ Grade 1 within 3 days of the initiation of maximal supportive care
- Any Grade 3 irAE, excluding colitis or pneumonitis, that does not downgrade to Grade 2 within 3
 days after onset of the event despite optimal medical management including systemic
 corticosteroids or does not downgrade to ≤ Grade 1 or baseline within 14 days
- Liver transaminase elevation > 8 × ULN or total bilirubin > 5 × ULN
- Any ≥ Grade 3 non-irAE, except for the exclusions listed below

The definition excludes the following conditions:

- Grade 3 fatigue lasting ≤ 7 days
- Grade 3 endocrine disorder (thyroid, pituitary, and/or adrenal insufficiency) that is managed
 with or without systemic corticosteroid therapy and/or hormone replacement therapy and the
 subject is asymptomatic
- Grade 3 inflammatory reaction attributed to a local antitumor response (e.g., inflammatory reaction at sites of metastatic disease, lymph nodes, etc.)
- Concurrent vitiligo or alopecia of any AE grade
- Grade 3 infusion-related reaction (first occurrence and in the absence of steroid prophylaxis) that resolves within 6 hours with appropriate clinical management

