6.4.1. Durvalumab + tremelimumab

Dose reductions are not permitted. In case of doubt, the Investigator should consult with the Study Physician.

Guidelines for the management of immune-mediated reactions, infusion-related reactions, and non-immune-mediated reactions for durvalumab monotherapy and durvalumab + tremelimumab are provided in the Dosing Modification and Toxicity Management Guidelines in Appendix 1.Error!

Reference source not found.

In addition, there are certain circumstances in which durvalumab and/or tremelimumab should be permanently discontinued.

Following the first dose of durvalumab +/- tremelimumab, subsequent administration of durvalumab +/- tremelimumab can be modified based on toxicities observed (see Appendix 1).

Based on the mechanism of action of durvalumab or tremelimumab leading to T-cell activation and proliferation, there is the possibility of observing immune related Adverse Events (irAEs) during the conduct of this study. Potential irAEs include immune-mediated enterocolitis, dermatitis, hepatitis, and endocrinopathies. Subjects should be monitored for signs and symptoms of irAEs. In the absence of an alternate etiology (e.g., infection or PD) signs or symptoms of enterocolitis, dermatitis, hepatitis, and endocrinopathy should be considered to be immune-related.

In addition, management guidelines for adverse events of special interest (AESIs) are detailed in Section 9.1.3. All toxicities will be graded according to NCI CTCAE v4.0

7. Restrictions During the Study and Concomitant Treatment(s)

The following restrictions apply while the patient is receiving study treatment and for the specified times before and after:

Female patient of child-bearing potential

Females of childbearing potential who are sexually active with a non-sterilized male partner must use at least 1 **highly** effective method of contraception (Table 3) from the time of screening and must

18 November 2020 Page **79** of **164**

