		 Initial work-up may include clinical evaluation, monitoring of oxygenation via pulse oximetry (resting and exertion), laboratory work-up, and high- resolution CT scan.
		 Consider Pulmonary and Infectious Disease Consults.
Grade 1	No dose modifications	For Grade 1 (radiographic changes only):
(asymptomatic, clinical or diagnostic observations only; intervention not indicated)	required. However, consider holding study drug/study regimen dose as clinically appropriate and during diagnostic work-up for other etiologies.	 Monitor and closely follow up in 2 to 4 days for clinical symptoms, pulse oximetry (resting and exertion), and laboratory work-up and then as clinically indicated. Consider Pulmonary and Infectious Disease consults.
Grade 2	Hold study drug/study	For Grade 2 (mild to moderate new
(symptomatic;	regimen dose until Grade	symptoms):
medical intervention	2 resolution to Grade ≤1.If toxicity worsens,	 Monitor symptoms daily and consider hospitalization.
indicated; limiting instrumental	then treat as Grade 3 or Grade 4. • If toxicity improves	 Promptly start systemic steroids (e.g., prednisone 1 to 2 mg/kg/day PO or IV equivalent).
ADL)	to Grade ≤1, then the decision to reinitiate study drug/study	 Reimage as clinically indicated, consider Chest CT with contrast and repeat in 3-4 weeks.
	regimen will be based upon treating physician's clinical judgment and after completion of steroid	 If no improvement within 3 to 5 days, additional workup should be considered and prompt treatment with IV methylprednisolone 2 to 4 mg/kg/day started
	taper.	 If still no improvement within 2 to 3 days despite IV methylprednisolone at 2 to 4 mg/kg/day, promptly start immunosuppressive therapy such as TNF inhibitors (e.g., infliximab at 5 mg/kg IV once, may be repeated at 2 and 6 weeks after initial dose at the discretion of the treating provider). Caution: It is important to rule out sepsis and refer to

18-Nov-2020 Page **130** of **164**

			infliximab label for general guidance before using infliximab.
			 Once the patient is improving, gradually taper steroids over ≥28 days and consider prophylactic antibiotics, antifungals, or anti-PJP treatment (refer to current NCCN guidelines for treatment of cancer- related infections)^a
			 Consider Pulmonary and Infectious Disease consults.
			 Consider, as necessary, discussing with study physician.
	Grade 3 or 4	Permanently discontinue	For Grade 3 or 4 (severe or new

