over baseline per	resolution to		volume and maintain hydration.	
day;	Grade ≤1; study	_	Urgent GI consult and imaging	
Grade 4 Diarrhea:	drug/study	_	and/or colonoscopy as appropriate.	
life threatening	regimen can be	_	If still no improvement within 2 days continue steroids and	
consequences)	resumed after		promptly add further	
(Grade 3 Colitis:	completion of		immunosuppressives (e.g., infliximab at 5 mg/kg IV, may be	
severe abdominal	steroid taper.		repeated at 2 and 6 weeks after	
pain, change in	Permanently		initial dose at the discretion of the	
bowel habits,	discontinue		treating provider). Caution : Ensure GI consult to rule out bowel	
medical	study drug/study		perforation and refer to infliximab	
intervention	regimen for		label for general guidance before using infliximab. If perforation is	
indicated,	Grade 3 if		suspected, consult a surgeon	
peritoneal signs;	toxicity does not improve to		experienced in abdominal surgery	
Grade 4 Colitis:	Grade ≤1 within	_	immediately without delay.	
life-threatening	14 days.	_	Once the patient is improving, gradually taper steroids over ≥28	
consequences,	•		days and consider prophylactic	
urgent	-Permanently discontinue		antibiotics, antifungals, and anti- PJP treatment (refer to current	
intervention	discontinue study drug for		NCCN guidelines for treatment of	
indicated)	1) Grade 3 colitis in			

Page **133** of **164** 18-Nov-2020

IND #134339

	(Grade 3 Perforation: severe symptoms, elective* operative intervention indicated; Grade 4 Perforation: life- threatening consequences, urgent intervention indicated)	patients treated with CTLA-4 inhibitors or 2) Any grade large intestine perforation/Intestinal perforation in any patient treated with ICI. Grade 4 Permanently discontinue study drug/study regimen.	cancer-related infections [Category 2B recommendation]). ^a
	*This guidance anticipates that Grade 3 operative interventions of perforations are usually not elective		
Hepatitis (elevated LFTs) Infliximab should not be used for management of immune-related hepatitis.	Any Elevations in AST, ALT or TB as Described Below	General Guidance	 For Any Elevations Described: Monitor and evaluate liver function test: AST, ALT, ALP, and TB. Evaluate for alternative etiologies (e.g., viral hepatitis, disease progression, concomitant medications).

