	-Hold study drug/study regimen until resolution to Grade ≤1 or baseline.	 Promptly initiate empiric IV methylprednisolone 1 to 2 mg/kg/day or equivalent.
	-If toxicity improves to	 Consider hospitalization.
	Grade ≤1 or baseline, then resume drug/study	 Monitor extent of rash [Rule of Nines].
	regimen after completion	 Consider skin biopsy (preferably more than 1) as clinically feasible.
	of steroid taper. -If toxicity worsens, then treat as Grade 4.	 Once the patient is improving, gradually taper steroids over ≥28 days and consider prophylactic antibiotics, antifungals, and anti- PJP treatment (refer to current NCCN guidelines for treatment of
	For Grade 4:	cancer-related infections). ^a
	Permanently discontinue	 Consider, as necessary, discussing with study physician.

18-Nov-2020 Page **141** of **164**

IND #134339

Endocrinopathy	Any Grade	General Guidance	For Any Grade:
(e.g., hyperthyroidism, thyroiditis,	(depending on the type of		 Consider consulting an endocrinologist for endocrine events.
hypothyroidism, Type 1 diabetes mellitus,	endocrinopathy, refer to NCI		 Consider, as necessary, discussing with study physician.
hypophysitis, hypopituitarism, and adrenal insufficiency; exocrine event of amylase/lipase increased also included in this	CTCAE v4.03 for defining the CTC grade/severity)		 Monitor patients for signs and symptoms of endocrinopathies. Non-specific symptoms include headache, fatigue, behavior changes, changed mental status, vertigo, abdominal pain, unusual bowel habits, polydipsia, polyuria, hypotension, and weakness.
section)			 Patients should be thoroughly evaluated to rule out any alternative etiology (e.g., disease progression including brain metastases, or infections).
			 Depending on the suspected endocrinopathy, monitor and evaluate thyroid function tests: TSH, free T3 and free T4 and other relevant endocrine and related labs (e.g., blood glucose and ketone levels, HgA1c).
			 Investigators should ask subjects with endocrinopathies who may require prolonged or continued hormonal replacement, to consult their primary care physicians or endocrinologists about further monitoring and treatment after completion of the study.
			 If a patient experiences an AE that is thought to be possibly of autoimmune nature (e.g., thyroiditis, pancreatitis, hypophysitis, or diabetes insipidus) the investigator should send a blook sample for appropriate autoimmune antibody testing.

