Grade 3 or 4	For Grade 3 or 4: Permanently discontinue study drug/study regimen.	_	For Grade 3 or 4: Manage severe infusion-related reactions per institutional standards (e.g., IM epinephrine, followed by IV diphenhydramine and ranitidine, and IV glucocorticoid).

CTCAE Common Terminology Criteria for Adverse Events; IM intramuscular; IV intravenous; NCI National Cancer Institute.

18-Nov-2020 Page **154** of **164**

Non-Immune-Mediated Reactions			
Severity Grade of the Event (Refer to NCI CTCAE applicable version in study protocol for defining the CTC grade/severity)	Dose Modifications	Toxicity Management	
Any Grade	Note: Dose modifications are not required for AEs not deemed to be related to study treatment (i.e., events due to underlying disease) or for laboratory abnormalities not deemed to be clinically significant.	Treat accordingly, as per institutional standard.	
Grade 1	No dose modifications.	Treat accordingly, as per institutional standard.	
Grade 2	Hold study drug/study regimen until resolution to ≤Grade 1 or baseline.	Treat accordingly, as per institutional standard.	
Grade 3	Hold study drug/study regimen until resolution to ≤Grade 1 or baseline. For AEs that downgrade to ≤Grade 2 within 7 days or resolve to ≤Grade 1 or baseline within 14 days, resume study drug/study regimen administration. Otherwise, discontinue study drug/study regimen.	Treat accordingly, as per institutional standard.	
Grade 4	Discontinue study drug/study regimen (Note: For Grade 4 labs, decision to discontinue should be based on accompanying clinical signs/symptoms, the Investigator's clinical judgment, and consultation with the	Treat accordingly, as per institutional standard.	

Note: As applicable, for early phase studies, the following sentence may be added: "Any event greater than or equal to Grade 2, please discuss with Study Physician."

AE Adverse event; CTCAE Common Terminology Criteria for Adverse Events; NCI National Cancer Institute.

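### Sections 4.4 and 6.3 end study drug after any DLT, but Appendix 1, where 6.4.1 sends later dosing decisions, says to resume after three kinds of event that can be DLTs

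*Combined protocol and SAP*

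**What the plan says.** Section 4.4 lists the events after which a patient receives no more investigational product. One entry is "Dose-limiting toxicity (See Section 6.3 for definition of DLT". Section 6.3 gives the same consequence: "A patient who experiences a DLT will be permanently discontinued from treatment and will proceed to surgery after standard preoperative evaluation".

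Section 6.3 defines DLTs broadly. They include:
- "Any ≥ Grade 3 non-irAE, except for the exclusions listed below";
- a Grade 3 immune-related event (colitis and pneumonitis have their own entries) that is not down to Grade 2 in 3 days, or not down to Grade 1 or baseline in 14 days;
- transaminases above 8 x ULN or total bilirubin above 5 x ULN.

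Section 6.4.1 then says that doses after the first "can be modified based on toxicities observed (see Appendix 1". It adds that some situations call for permanent discontinuation, but names neither DLT nor Section 4.4.

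Appendix 1 adds two general conditions for permanent discontinuation to its grade-based rules: failure to reduce steroids within 12 weeks, and Grade 3 recurrence of an immune-mediated event after dosing has resumed. DLT is not among them.

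**The concern.** At the moment of a re-dosing decision, 6.4.1 points the investigator to a table that in places gives the opposite instruction to 4.4 and 6.3. The opening guidance in 6.4 leans the same way: it favours continuing the same dose when symptoms resolve promptly, again with no exception for DLTs. At stake is renewed checkpoint inhibition shortly before lung resection, in a patient whose event the protocol says ends study therapy.

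**Working it through.** The plan states no figure on this point. The check sets the texts side by side, then asks whether a resumed dose could fit the schedule.

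**Rows where Appendix 1 says to resume**

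| Event | Section 6.3 | Appendix 1 |
|---|---|---|
| Treatment-related Grade 3 non-immune event, not on the 6.3 exclusion list | DLT; recovery does not remove it | If down to Grade 2 in 7 days, or to Grade 1 or baseline "within 14 days, resume study drug/study regimen administration" |
| Grade 3 rash | DLT if the 3-day or 14-day limit is missed | Hold, with no time limit; on reaching "Grade ≤1 or baseline, then resume drug/study" regimen after the steroid taper |
| Liver enzyme or bilirubin rise | DLT if a Grade 3 immune rise is not down to Grade 2 in 3 days, or if above 8 x ULN (bilirubin 5 x ULN) | Resume if recovered within 14 days and after taper; permanent stop at 8 x ULN (bilirubin 5 x ULN), or at those multiples of baseline if baseline is abnormal |

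**Rows where Appendix 1 only permits resumption.** The Grade 3 colitis stop that applies whatever the recovery is confined to "patients treated with CTLA-4 inhibitors or 2) Any grade large intestine perforation/Intestinal perforation in any patient treated with ICI", so in cohort 1 dosing may restart after recovery within 14 days. For Grade 2 pneumonitis that improves, "then the decision to reinitiate study drug/study" regimen is left to the physician, even if it lasted beyond the 3 days that make it a DLT. Some Grade 4 endocrine and laboratory events are also left open. In all these rows, stopping satisfies both texts.

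**Size of the liver gap.** Section 4.1 admits AST/ALT up to 2.5 x ULN and bilirubin up to 1.5 x ULN (Gilbert's syndrome aside). With an abnormal baseline, the Appendix 1 stop in multiples of ULN is:
- transaminases, 8 x baseline: 8 x 1.5 = 12; 8 x 2.0 = 16; 8 x 2.5 = 20, against 8 in Section 6.3;
- bilirubin, 5 x baseline: 5 x 1.25 = 6.25; 5 x 1.5 = 7.5, against 5 in Section 6.3.

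Values in between are DLTs that fall in the row that says to resume, unless Appendix 1's Hy's law stop applies.

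**Can a resumed dose fit?** Inputs: doses on days 1, 30 and 60; 25 fractions at 5 per week; surgery 6-8 weeks after radiation (Section 6.2). Dose 2 may be deferred only within radiation, and dose 3 only up to planned surgery (Section 3.1.5). Assumptions: radiation starts on a Monday and is not interrupted, and the taper lasts 28 days, the Appendix 1 minimum. The last fraction is then day 1 + 28 + 4 = 33, and surgery falls between 33 + 42 = day 75 and 33 + 56 = day 89.

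- *Non-immune event, onset day 2.* Grade 2 by 6 days and Grade 1 by 10 days: recovered on day 2 + 10 = 12. Grade 2 by 8 days and Grade 1 by 14 days: day 2 + 14 = 16. Both are DLTs, both meet the resume rule, and dose 2 on day 30 is still ahead.
- *Rash, onset day 31.* Grade 2 at 4 days and Grade 1 at 10 days: the taper ends between 31 + 4 + 28 = day 63 and 31 + 10 + 28 = day 69, depending on when it starts. Grade 2 at 6 days and Grade 1 at 21 days: between 31 + 6 + 28 = day 65 and 31 + 21 + 28 = day 80. All fall before day 89, so dose 3 could be given.
- *Rash, onset day 2.* Grade 2 at 4 days: the taper ends no earlier than 2 + 4 + 28 = day 34, after radiation. The dose 2 window has closed and therapy ends anyway under 3.1.5.

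**The case against.** The strongest reply is that the hierarchy is clear enough. Sections 4.4 and 6.3 are specific to this trial, mandatory and in agreement. Appendix 1 is a general drug-class guideline, with pediatric and hepatocellular carcinoma entries that cannot apply here. It calls its own management advice recommended, and Section 9.1.3 presents it as an aid to clinical judgment. The pointer in 6.4.1 is permissive, and its remark about permanent discontinuation shows that Appendix 1 was not meant as the full stopping list.

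This stands as a reason to read 4.4 as controlling. It does not remove the conflict: the remark in 6.4.1 does not identify DLT or 4.4, and the three rows use direct instructions.

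Safeguards also count: consultation with the Study Physician in case of doubt (6.4.1), recovery to Grade 1 or less before surgery (6.3), weekly record review (3.1.6.2), weekly investigator meetings (12.1) and continuous DLT monitoring (12.2.2). They lower the chance of an unintended dose, but none says which text applies.

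The non-immune row is also narrower than it looks. Events clearly due to another cause are not DLTs, and inflammatory events without a clear alternative cause are treated as immune (9.1.5).

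A reader might infer that Appendix 1 overrides 4.4, or that every mismatched row is a contradiction. Neither follows. Nothing gives Appendix 1 precedence, and in the permissive rows a stop under 4.4 is consistent with both texts.

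**Conclusion.** The inconsistency is real and should be corrected. For three kinds of event, two parts of the protocol give opposite dosing instructions, and no sentence ranks them.

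Its reach is limited. There are only three doses. Quickly recovered non-immune events can affect dose 2 or dose 3. Events that need a taper of at least 28 days mainly affect dose 3; this rests on the schedule assumptions above, and longer radiation would keep the dose 2 window open longer.

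The documents give no rate for these events at DLT severity, and none is assumed. Section 1.13.3 lists rash and raised ALT among events of any grade in at least 10% of patients on the combination. That shows relevance to cohort 2, not a DLT rate. The 20 x ULN and 7.5 x ULN figures are ceilings for a patient who enters exactly at the eligibility limit.

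It would be wrong to infer that the safety monitoring is compromised. An event is a DLT under 6.3 whether or not dosing resumes, so DLT counts and Table 10.1 do not change.

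**What to change.** Add one sentence to Section 6.4.1: *Any event meeting the Section 6.3 DLT definition permanently ends durvalumab and tremelimumab (Section 4.4), whatever resumption Section 6.4 or Appendix 1 otherwise allows; Appendix 1 resumption rules apply only to non-DLT events.*

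A matching note at the head of Appendix 1 is optional. If the team does want dosing to continue after a particular event, such as an isolated Grade 4 lipase rise without pancreatitis, that exception belongs in the 6.3 exclusion list, so that DLT status and dosing stay aligned.

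The cost is a protocol amendment with IRB approval (Section 13.4). There are no new procedures. A few patients with recovered events would forgo a remaining dose, as 4.4 and 6.3 already require.

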PLEASE SEE shaded area immediately below this section to find guidance for management of "Hepatitis (elevated		 No dose modifications. If it worsens, then treat as described for elevations in the row below. 	_
LFTS)" in HCC patients	AST or ALT >3.0×ULN and ≤5.0 if baseline normal, >3-5×baseline if baseline abnormal; and/or TB>1.5×ULN	Hold study drug/study regimen dose until resolution to AST or ALT ≤3.0×ULN and/or TB ≤1.5×ULN if baseline normal, or to AST or ALT ≤3.0×baseline and/or TB ≤1.5×baseline if baseline abnormal. If toxicity worsens, then treat as described	Regular and frequent checking of LFTs (e.g., every 1 to 2 days) until elevations of these are improving or resolved. - If no resolution to AST or ALT≤3.0×ULN and/or TB ≤1.5×ULN if baseline normal, or to AST or ALT ≤3.0×baseline and/or TB≤1.5×baseline if baseline abnormal, in 1 to 2 days, consider, as necessary, discussing with study physician. - If event is persistent (>2 to 3 days) or worsens, promptly start

18-Nov-2020 Page **134** of **164**

IND #134339

and ≤3.0×ULN if baseline normal, >1.5-3.0×baseline if baseline abnormal for elevation in the row below.

If toxicity improves to AST or ALT ≤3.0×ULN and/or TB ≤1.5×ULN if baseline normal, or to AST or ALT ≤3.0×baseline and/or TB ≤1.5×baseline if baseline abnormal, resume study drug/study regimen after completion of steroid taper.

prednisone 1 to 2 mg/kg/day PO or IV equivalent .

AST or
ALT >5.0×ULN
if baseline
normal,
>5×baseline if
baseline
abnormal;
and/or
TB >3.0×ULN if
baseline normal;
>3.0×baseline if
baseline

For elevations in transaminases ≤8×ULN and/or in TB ≤5×ULN if baseline normal, or for elevations in transaminases ≤8×baseline and/or TB ≤5×baseline if baseline abnormal:

- Hold study drug/study regimen dose until resolution to AST or ALT ≤3.0×ULN and/or TB ≤1.5×ULN if baseline normal, or to AST or ALT ≤3.0×baseline and/or TB ≤1.5×baseline if baseline abnormal
- Resume study drug/study regimen if elevations downgrade to AST or ALT ≤3.0×ULN and/or TB ≤1.5×ULN if baseline normal, or to AST or ALT ≤3.0×baseline and/or TB ≤1.5×baseline if baseline abnormal, within 14 days and after completion of steroid taper.
- Permanently discontinue study drug/study regimen if the elevations do not downgrade as described in bullet above within 14 days

For elevations in transaminases >8×ULN or

- Promptly initiate empiric IV methylprednisolone at 1 to 2 mg/kg/day or equivalent.

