- If still no improvement within 2 to 3 days despite 1 to 2 mg/kg/day methylprednisolone IV or equivalent, promptly start treatment with immunosuppressive therapy (i.e., mycophenolate mofetil 0.5-1 g every 12 hours then taper in consultation with hepatology consult). Discuss with study physician if mycophenolate is not available. Infliximab should NOT he used.
- Request Hepatology consult, and perform abdominal workup and imaging as appropriate.
- Once the patient is improving, gradually taper steroids over ≥28 days and consider prophylactic antibiotics, antifungals, and anti-PJP treatment (refer to current NCCN guidelines for treatment of cancer-related infections).^a

18-Nov-2020 Page **135** of **164**

IND #134339

elevations in TB >5×ULN if baseline normal, or for elevations in transaminases >8×baseline and/or TB >5×baseline if baseline abnormal, permanently discontinue study drug/study regimen. Permanently discontinue study drug/study regimen for any case meeting Hy's law criteria (AST and/or $ALT > 3 \times ULN +$ bilirubin >2 × ULN without initial findings of cholestasis (i.e., elevated alkaline P04) and in the absence of any alternative cause.b

Hepatitis (elevated LFTs)

Infliximab should not be used for management of immune-related hepatitis.

THIS shaded area is guidance *only* for management of "Hepatitis (elevated LFTs)" in HCC patients

See instructions at bottom of shaded area if transaminase rise is not isolated but (at any time) occurs in setting of either increasing bilirubin or signs of DILI/liver decompensation

Any Elevations in AST, ALT or TB as Described Below

General Guidance

For Any Elevations Described:

- Monitor and evaluate liver function test: AST, ALT, ALP, and TB.
- Evaluate for alternative etiologies (e.g., viral hepatitis, disease progression, concomitant medications, worsening of liver cirrhosis [e.g., portal vein thrombosis]).
 - For HBV+ patients: evaluate quantitative HBV viral load, quantitative HBsAg, or HBeAg
 - For HCV+ patients: evaluate quantitative HCV viral load
 - Consider consulting
 hepatologist/Infectious Disease
 specialist regarding
 change/implementation in/of
 antiviral medications for any
 patient with an elevated HBV viral
 load >2000 IU/ml
 - Consider consulting hepatologist/Infectious Disease specialist regarding change/implementation in/of antiviral HCV medications if HCV viral load increased by ≥2-fold
- For HCV+ with HBcAB+: Evaluate for both HBV and HCV as above

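### A Hy's law case below Grade 3 forces a permanent stop under Appendix 1 but does not count toward the Bayesian safety rule

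*Combined protocol and SAP*

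**What the plan says.** **Appendix 1, hepatitis rows for patients without hepatocellular carcinoma.** Three situations end study drug for good:

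- The highest values: "elevations in TB >5×ULN if baseline normal, or for elevations in transaminases >8×baseline" and the matching limits in that row (transaminases above 8×, bilirubin above 5×).
- The tier above 5×/3× but within 8×/5×, if it persists: "Permanently discontinue study drug/study regimen if the elevations do not downgrade as described in bullet above within 14 days".
- Hy's law: "Permanently discontinue study drug/study regimen for any case meeting Hy's law criteria". Appendix 1 defines this as AST and/or ALT above 3×ULN with bilirubin above 2×ULN, "without initial findings of cholestasis (i.e., elevated alkaline P04) and in the absence of any alternative cause".

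**Section 6.3.** The general DLT test is Grade 3 or higher. The liver-specific entry is "Liver transaminase elevation > 8 × ULN or total bilirubin > 5 × ULN". A generic entry for Grade 3 immune-related events in any organ other than colitis or pneumonitis includes persistence: "corticosteroids or does not downgrade to ≤ Grade 1 or baseline within 14 days". The one listed event below Grade 3 is Grade 2 pneumonitis that does not resolve. Hy's law is not named, and no clause turns a permanent discontinuation into a DLT. The window runs "until 30 days after surgical resection or 100 days following the last dose of study therapy, whichever occurs later".

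**Section 12.2.2.** The monitored events are Grade 3-4 toxicities of the 6.3 types, with liver named first. Accrual is suspended when the posterior probability of a rate above 25% reaches 70%, under a Beta(0.05, 0.95) prior.

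**Sections 9.3.6 and 9.3.12.2.** A potential Hy's law case (at least 3× with at least 2×, whatever the alkaline phosphatase) may need to be reported as an SAE. It must be reported within 24 hours unless an unrelated diagnosis is confirmed. Dosing is interrupted at once if no definitive diagnosis is established.

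**Section 6.2.3.3.** A patient who misses planned doses and goes to surgery is replaced, with continued safety follow-up.

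**The concern.** The protocol treats confirmed Hy's law as serious enough to end treatment, yet the statistical rule meant to react to toxicity in real time does not clearly count it. With 16 evaluable patients per cohort and a first boundary at 2 events in 3 or 4 patients, one uncounted event can decide whether accrual continues. The same stop can lead to replacement, so a serious liver injury might leave the 16-patient denominator without ever being a DLT. Whether it counts could turn on how the investigator records it: two moderate laboratory values, or one diagnosis graded 3.

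**Working it through.** **1. Is there a route into the count?** Take ALT 4×ULN, bilirubin 2.5×ULN, normal alkaline phosphatase and no other cause.

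| Provision | Result |
|---|---|
| Appendix 1, Hy's law | Permanent stop |
| 9.3.12.2 | 24-hour report; dosing interrupted |
| 6.3 liver entry (>8×/>5×) | Not met |
| 6.3 Grade 3 immune-related entry | Not met if both values are below Grade 3 |
| 6.3 general rule | Not met, unless the diagnosis itself is graded 3 or more |
| 12.2.2 investigator-judgment clause | Limited to Grade 3-4 |
| 12.2.2 pointer to section 9.2 | 9.2 holds severity and causality scales, not an event list |

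The documents print no CTCAE liver cut-offs. I assume Grade 3 starts above 5×ULN for transaminases and above 3×ULN for bilirubin. The Appendix 1 row breaks fit this: the lower row is "AST or ALT >3.0×ULN and ≤5.0 if baseline normal", with bilirubin above 1.5× up to 3×, but the rows carry no grade labels.

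**2. Reproduce the stated rule.** With x events in n patients, suspend if P(p > 0.25) ≥ 0.70 under Beta(0.05 + x, 0.95 + n − x).

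- Prior P(p > 0.25) = 7.0% (stated: about 7%).
- Boundary: 2 of 3-4, 3 of 5-7, 4 of 8-11, 5 of 12-14, 6 of 15-16. This agrees with every cell printed in Table 10.1, which omits 12-15 patients.
- Exact stopping probability, looking after each patient from the 3rd to the 16th:

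| True rate | Recomputed | Table 10.2 |
|---|---|---|
| 0.15 | 16.3% | 15.8% |
| 0.20 | 29.3% | 29.3% |
| 0.25 | 44.3% | 43.1% |
| 0.30 | 59.4% | 60% |
| 0.35 | 72.8% | 72.8% |

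The rule is numerically sound. The question is only which events enter it.

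**3. Effect of one uncounted case at the boundary.**

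| Patients | Posterior without the case | Posterior with the case |
|---|---|---|
| 4 | 1 event: 33.9%, continue | 2 events: 75.5%, suspend |
| 6 (planned pause) | 2 events: 55.2%, resume | 3 events: 84.1%, stay suspended |

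**4. Average effect.** Let h be the share of patients whose only qualifying event is a Hy's law case below Grade 3. The documents give no value, so h is assumed. Expected cases = 16h, and P(at least one) = 1 − (1 − h)^16. The rule then sees the true rate minus h.

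| h | Expected cases in 16 | P(≥1) | Stop at true 30% (59.4% if counted) | Stop at true 25% (44.3% if counted) |
|---|---|---|---|---|
| 0.5% | 0.08 | 7.7% | 58.0% | 42.8% |
| 1% | 0.16 | 14.9% | 56.5% | 41.2% |
| 2% | 0.32 | 27.6% | 53.5% | 38.2% |

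At h = 1% the loss is 59.4 − 56.5 = 2.9 points and 44.3 − 41.2 = 3.1 points.

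**The case against.** The best defence is that section 6.3 is a Grade 3 definition by design and that Hy's law has its own, more specific pathway. Under 9.3.12.2 the case is reported within 24 hours, followed by the investigator, and evaluated by the sponsor and the drug supplier. SAEs are part of the primary safety endpoint (12.2.1), records are reviewed weekly (3.1.6.2), investigators meet weekly (12.1), and section 3.2 allows early termination for the severity of a drug reaction without any count. An investigator who records a diagnosis, as 9.3.4 prefers, may grade it 3 and so bring it into the count. All of this stands, and it is why the point is minor. None of it places the event in Table 10.1.

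Three stronger readings are tempting but unsupported.

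- *That 6.3 was built to mirror the Appendix 1 liver stops and dropped one.* It has a single liver entry. The 14-day persistence case is caught only by a generic entry that also adds a 3-day test absent from Appendix 1. Other stops that can apply below Grade 3 (intestinal perforation and transverse myelitis of any grade, biopsy-proven myocarditis) are not named in 6.3 either, so a permanent stop is not this protocol's DLT test.
- *That the roughly half of the DLT window after surgery is exposure to this gap.* No doses remain to be stopped by then, adjuvant chemotherapy may have started, and both definitions exclude events with another cause.
- *That up to 12 patients could accrue between six-monthly DSMB reviews before anyone looks.* Section 12.2.2 holds each cohort at 6 patients for safety evaluation, and the weekly reviews run throughout.

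**Conclusion.** The gap is real and narrow. A confirmed Hy's law case whose laboratory values stay below Grade 3 ends treatment under Appendix 1 and triggers a 24-hour report. As written, it does not count toward the Bayesian safety rule unless the diagnosis is graded 3 or more, and the patient may be replaced. The finding rests on the assumed Grade 3 cut-offs of 5×/3×ULN. Its size rests on an assumed rate: about 3 points of stopping probability per percentage point of such cases, at true toxicity rates of 25-30%. It changes a decision only when the case is the boundary event, and the consequence is a temporary suspension with team review. A reader should not infer that these cases go unreported or that Tables 10.1 and 10.2 are wrong where printed. This is an inexpensive improvement to consider, not a required correction.

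**What to change.** Two edits are needed, because 12.2.2 filters by grade and would still exclude an event added to 6.3 alone.

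1. **Section 6.3**, add to the DLT list: *confirmed Hy's law case as defined in Appendix 1 (AST or ALT >3×ULN with total bilirubin >2×ULN, without initial cholestasis and without alternative cause), regardless of grade.*
2. **Section 12.2.2**, add: *potential cases reported under 9.3.12.2 are adjudicated against this definition; if confirmed, they count toward Table 10.1 even if the patient is replaced.*

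The adjudication step matters because 9.3.12.2 uses a wider screen (≥3×/≥2×, irrespective of alkaline phosphatase) than Appendix 1. Without it, reported and counted cases would differ with no stated reason.

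The cost is amendment wording in two places, with no new tests or visits, since Table 7 already requires transaminases, alkaline phosphatase and bilirubin to be assessed together. Accrual would be suspended slightly more often. If 1% of patients have such a case on top of other DLT rates of 15%, 20% or 25%, the stopping probability rises from 16.3% to 18.6%, from 29.3% to 32.2%, or from 44.3% to 47.4%.
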